Power was computed for an effect size (d) of 0.37, a small-medium effect size to be conservative, based on similar intervention studies in similar facilities comparing groups in terms of high levels of medication adherence and changes in HIV risk behavior.^[4] The computations assume an intraclass correlation (ICC) of 0.500, as we assume conservatively large dependence within participant overtime. Over a 44-month period, 300 participants taking PrEP and enrolled in methadone-maintenance treatment at the APT Foundation (see letter of support) will be recruited and randomly assigned to the two study cells (150 per cell). The criterion for significance (alpha) has been set at 0.05. The test is 2-tailed, which means that an effect in either direction will be interpreted. Given these assumptions (for the effect size, ICC), criteria (for alpha and tails), and plans (for the number of clusters and sample size within cluster), the study will have power of 98.5% to yield a statistically significant result. These same assumptions (for the ICC), and plans (for the number of subjects and time points within subject), the study will allow us to report the effect size (d) with a standard error of approximately 0.089. In order to maintain that power level, we must 288 retain patients at post-intervention, 276 at 3-month follow-up, 258 patients at 6-month follow-up, and 224 patients at 9-month follow-up. Even in the event that only 71% of participants complete the final 9-month follow-up assessment, which would be a conservative estimate based on the previous randomized controlled trials in the same facility among the same patient population, the proposed ample size will still provide sufficient power (94.5%) to detect the expected range of effect sizes.

For EACH Participant Population State Describe the Study Population(s): [Describe the participant population(s) including gender, ethnicity, income, level of education and age range.]

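### The two attrition power figures (98.5% at the retention targets, 94.5% at 71% completion) do not come out of any single calculation tried; on either analysis set one of them is off by about 4 points

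*Combined protocol and SAP*

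**What the plan says.** All the figures are in one paragraph of the combined protocol and SAP, the power and sample-size justification that precedes the description of the study population.

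- Effect size: "Power was computed for an effect size (d) of 0.37".
- Correlation: "The computations assume an intraclass correlation (ICC) of 0.500". The paragraph explains this as dependence within a participant over time, so participants are the clusters and visits are the units within them.
- Size: 300 participants in two equal arms of 150.
- Test: two-sided at the 5% level. On sidedness the paragraph says: "The test is 2-tailed, which means that an effect in either direction will be interpreted".
- Result: power 98.5%, with a standard error for d of about 0.089.
- Retention: "In order to maintain that power level, we must 288 retain patients at post-intervention, 276 at 3-month follow-up, 258 patients at 6-month follow-up". For the 9-month visit the target is 224.
- Fallback: the case considered is "Even in the event that only 71% of participants complete the final 9-month follow-up assessment". Of that case the paragraph claims that "the proposed ample size will still provide sufficient power (94.5%) to detect the expected range of effect sizes".

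The paragraph does not give the number of time points. It also does not say whether the attrition figures count only people who complete every visit or all visits observed. The assessment schedule in the study design section lists five: baseline, post-intervention (T8), T20, T32 and T44.

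**The concern.** The two attrition sentences stand next to each other and describe nearly the same situation at the last visit. The target is 224 (224/300 = 74.7%), and the fallback is 71%, which is 213. Losing 11 more people out of 300 at one of several correlated visits should hardly change power, yet the stated power drops from 98.5% to 94.5%. A gap of that size suggests that the two sentences were calculated in different ways.

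The retention counts are written as requirements, and 71% is called a conservative estimate. A reader cannot tell what power goes with either scenario, or which participants the calculation includes. If the power is later restated for a chosen primary visit, the same ambiguity would carry over.

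**Working it through.** **Inputs.** d = 0.37, ICC ρ = 0.5, N = 300 in two equal arms and two-sided α = 0.05 come from the power paragraph. The number of time points, m = 5, comes from the assessment schedule and is an inference, tested in step 1. Losses are assumed to be split equally between arms.

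**Formulae.** A participant seen k times contributes information k / (1 + (k − 1)ρ). At ρ = 0.5 this is 1, 1.333, 1.5, 1.6 and 1.667 for k = 1 to 5. With total information I over both arms, SE(d) = √(4/I) and power ≈ Φ(d/SE − 1.96). Noncentral t values (df = N − 2) are given where they differ visibly.

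**Step 1: reproduce the plan's figure.** With no loss and m = 5, I = 300 × 5/3 = 500. SE = √(4/500) = 0.0894. d/SE = 4.137. Power = Φ(2.177) = 98.5%. Both stated figures are matched. With m = 4 (post-baseline visits only), I = 300 × 1.6 = 480, SE = 0.0913 and power = 98.2%, so neither is matched to the precision given. Five time points and no loss is therefore the basis that fits.

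**Step 2: completers only, m = 5.**
- 224: I = 373.3, SE = 0.1035, power 94.7% (normal) or 94.5% (noncentral t).
- 213: I = 355.0, SE = 0.1061, power 93.6% (normal) or 93.4% (noncentral t).
- Difference: about 1 point.

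**Step 3: all observed visits, monotone loss, m = 5.**
- Targets 300/288/276/258/224. The numbers seen 1, 2, 3, 4 and 5 times are 12, 12, 18, 34 and 224. I = 12 + 16 + 27 + 54.4 + 373.3 = 482.7, SE = 0.0910, power 98.23%.
- Same, with 213 at the last visit. The numbers are 12, 12, 18, 45 and 213. I = 12 + 16 + 27 + 72 + 355 = 482.0, SE = 0.0911, power 98.22%.
- Difference: about 0.01 point.

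**Step 4: compare with the plan.**

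| Scenario | Stated | Completers only | All observed visits |
|---|---|---|---|
| Targets, 224 at 9 months | 98.5% | 94.5–94.7% | 98.2% |
| 71%, 213 at 9 months | 94.5% | 93.4–93.6% | 98.2% |
| Drop between the two | 4.0 points | about 1 point | about 0.01 point |

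On completers, the first stated figure is 3.8 to 4.0 points too high and the second is about 1 point too high. On all observed visits, the first is 0.3 points too high and the second is 98.2 − 94.5 = 3.7 points too low.

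**Step 5: sensitivity.** The plan gives no earlier-visit counts for the 71% case. If all 300 have a baseline and only 213 attend every later visit, I = 87 × 1 + 213 × 5/3 = 442.0 and power is 97.3%, still well above 94.5%. With four post-baseline visits, completers give 93.9% (normal) or 93.7% (noncentral t) at 224, and 92.7% or 92.5% at 213. All observed visits on that basis give 97.4% for both.

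**The case against.** Each sentence is defensible taken alone. The justification models time points within participants and sets a separate target for each visit, which suggests that partial follow-up counts. On that reading the targets give 98.2%, and calling this the same power level as 98.5% is no material misstatement. Equally, 213 completers give 93.4–93.6%, about 1 point from the stated 94.5%. Both observations stand. They do not rescue the pair, because each needs a different analysis set.

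A further defence is that the 71% scenario may involve heavier loss at earlier visits too. On five time points, the extreme case in step 5 still gives 97.3%. On four post-baseline visits, early loss could bring power anywhere between 92.7% and 97.4%, a range that includes 94.5%. But that basis gives 97.4% at the targets, and it does not reproduce 98.5% or SE 0.089 with no loss.

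Three stronger readings are tempting, and the documents do not support them.

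- A reader might infer that on the plan's own basis the targets yield only 94.5%, so that type II error rises from 1.5% to 5.5% and there is no room for any loss. That holds only if all 76 people without a 9-month visit (300 − 224) are discarded, earlier visits included. The justification does not say so, and the targets of 288, 276 and 258 would then have no purpose.
- A reader might infer that 94.5% was calculated for 224 and attached to the 71% case by mistake. The match to one decimal depends on the noncentral t (94.51%); the normal approximation gives 94.7% at 224 and reaches 94.5% at 222. The plan does not name its formula, so this is a guess about the authors' working.
- A reader might infer that the sample size is too small. Nothing here shows that.

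**Conclusion.** The point holds in a limited form. No single basis tried gives both 98.5% at the targets and 94.5% at 71% completion. One of the two figures is off by about 4 points: the first is too high if only completers count, or the second is too low if all observed visits count. The documents do not show which.

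The conclusion rests on five time points (inferred, but confirmed by matching both 98.5% and SE 0.089), compound symmetry with ICC 0.5, equal loss between arms and, for the all-visits figures, monotone dropout with the earlier visits at their stated targets. It takes the plan's repeated-measures basis as given and says nothing about which visit should be primary.

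The practical effect is small. Power is about 93% or more in every scenario on the five-visit basis, and at least 92.5% if only the four post-baseline visits count. This is a correction to the stated figures and no threat to the design.

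**What to change.** In the power justification:

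1. State that 98.5% and SE 0.089 assume five time points per participant and no loss.
2. State whether the attrition figures use completers only or all observed visits, in line with the analysis that will be run.
3. Give both attrition scenarios by that one method.
   - All observed visits: 98.2% (SE 0.091) for both. Add the earlier-visit counts assumed in the 71% case; 98.2% takes them at 288/276/258.
   - Completers only: about 94.5% (SE 0.104) at 224 and about 93.5% (SE 0.106) at 213. Delete the opening clause of the retention sentence, which says that the targets preserve the 98.5%.
4. If power is restated for a particular primary visit, recalculate the attrition scenarios by the same method.

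The cost is one recalculation and a few sentences. No extra patients are needed and no procedure changes.

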Participants for trial will be included who are: 1) Are 18 years of age or older; 2) Meet DSM-V criteria for opioid-dependence and are enrolled in methadone maintenance drug treatment at the APT Foundation, Inc.; 3) Were confirmed to be HIV-negative and started on PrEP in the past week; 4) Report unsafe injection drug use practices or unprotected sex within the past 3 months; 5) Have a cell phone; 6) Are able to read and understand the questionnaires, ACASI, and informed consent form; 7) Available for the full duration of the study with no anticipated circumstances impeding participation (e.g., pending charges, jail term). Individuals unable to provide consent and who are actively suicidal, homicidal, or psychotic as assessed by trained research staff under the supervision of the PI who is a licensed clinical psychologist in Connecticut will be excluded.

We plan to recruit 60% men and 40% women (18 years or older) in order to adequately represent the proportion of men and women in the New Haven community. Recruiting 60% men and 40% women should pose no problem given that the men constitute 61% of the APT Foundation MMP (Methadone Maintenance Program), the patient population from which the subjects for the proposed studies will be recruited. However, given that women typically represent 39% of APT MMP population, we plan to increase our efforts to recruit women into the methadone treatment program by posting advertisements at the APT Foundation substance abuse treatment program.

Minorities. We plan to recruit 50% English-speaking minorities; 40% African American and 10% English-speaking Latino/Latina. These target figures are representative of African-Americans and Latino/ Latinas in the community.

Enrollment of UConn Students and/or Employees: [Will UConn students be enrolled? If so, describe if these students include those who any key research personnel teaches, or for whom any key research personnel has responsibility. Will UConn employees be enrolled? If so, describe if these employees

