Intervention Fidelity and Preventing Cross Contamination. We use several procedures to guard against potential threats to internal validity. First, as part of our NIDA-funded work, we have already developed detailed intervention manuals that include detailed session outlines and all other supporting materials needed to conduct the CHRP-BB sessions and the Control condition session have also been manualized. Second, facilitators will complete pre-session checklists and post-session quality assurance forms. Third, we will audiotape all intervention sessions to monitor the content and time allocation of intervention sessions. Using procedures from prior and ongoing intervention trials,^[19, 30, 31, 42] all sessions will be coded for protocol adherence. Fourth, intervention facilitators will meet with the project director and the PI for weekly clinical supervision. Meetings will focus on protocol adherence, resolving issues that arise in sessions, and managing potential “drift”. Study participants will not have contact with each other beyond their participation in routine drug treatment services. In addition, when we become aware of relationship partners enrolling in the study, we will force-randomize them to the same condition in order to avoid cross contamination and violation of group independence. If we find that relationship partners constitute more than 5% of participants, we will include couple status as a factor in our outcome analyses.

Data Analysis: [For all studies, specify the analytic techniques the researcher will use to answer the study questions. Indicate the statistical procedures (e.g. specific descriptive or inferential tests) that will be used and why the procedures are appropriate. For qualitative data, specify the proposed analytic approaches.]

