Main outcomes analysis plan: The framework for testing the study hypotheses will be to compare differences between the two conditions (CHRP-BB vs. Control) on the main outcome variables. Separate logistic regression models will be used to assess the log odds of having high levels of PrEP adherence and being free from injection or sexual transmission risk behaviors at T₄₄ post-intervention using intervention assignment as a binary coded predictor while controlling for any potential confounders. As an alternative analytical plan for assessing the impact of the two intervention arms on adherence to PrEP, we will use

questionnaires, and collection of urine sample is minimal and adds no risk beyond those normally associated with methadone maintenance treatment. Assessment measures and content of the intervention will involve sensitive and explicit topics related to sexual behavior and substance use. This is necessary given the nature of the intervention and practices that confer risk for HIV infection. However, participants may feel awkward or embarrassed when hearing about or being asked to provide information related to sexual activity. The consent procedure informs participants that sexual behaviors will be explicitly covered in measures and intervention content. Counseling staff will have been trained to observe for signs of subject emotional distress in relation to topic presentation and to employ techniques that prevent, reduce or minimize embarrassment, discomfort, or atypical distress.

Some participants may experience increased anxiety as a result of participating in the intervention. Realistic sensitization and accurate vulnerability self-appraisal are desirable and necessary to motivate behavior change efforts. The investigator is experienced in presenting risk reduction information in ways that link risk to avoidable and modifiable behaviors and risk reduction to the adoption of behavior changes. Counseling staff will observe participants for evidence of becoming overly anxious and will utilize techniques to assure that threat sensitization and vulnerability perceptions are realistic. Research staff will also be knowledgeable of social services that some participants may need, and will assist participants in accessing local resources in areas such as alcohol and other drug abuse treatment, entitlement, and supports for those in or leaving abusive relationships.

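### Minor: above 5% relationship partners, a couple-status factor adjusts the mean but, in the logistic models that can be read, does not model correlation between partners in the same arm

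*Combined protocol and SAP*

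**What the plan says.** Under Intervention Fidelity and Preventing Cross Contamination, the plan states that when staff learn of relationship partners enrolling, "we will force-randomize them to the same condition in order to avoid cross contamination and violation of group independence". It then sets a trigger: "If we find that relationship partners constitute more than 5% of participants", the response is "we will include couple status as a factor in our outcome analyses". With 300 participants planned, the trigger is more than 0.05 × 300 = 15 people.

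Under Main outcomes analysis plan, the visible model is logistic: "Separate logistic regression models will be used to assess the log odds of having high levels of PrEP adherence", with a parallel model for freedom from injection or sexual risk behavior. Arm is a binary predictor and confounders are covariates. A further analysis is announced, but the text stops before it is named: "As an alternative analytical plan for assessing the impact of the two intervention arms on adherence to PrEP, we will use".

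No visible text mentions a couple-level random effect, generalized estimating equations or cluster-robust variance. The only intraclass correlation given, 0.500 in the sample-size paragraph, describes repeated measures within a participant, not partners.

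**The concern.** Same-arm allocation prevents contamination between arms, but it turns each couple into a cluster of two inside one arm. If partners' outcomes are positively correlated, 300 people carry slightly less information than 300 independent people.

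A couple-status term takes the same value for every partnered participant. It shifts the expected outcome for that group and cannot say which two people are paired. Reading the term as one fixed effect per couple does not help either: both partners are in the same arm, so no couple contains an arm contrast.

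The contingency therefore responds to a dependence that it does not model. At stake are a slightly small standard error, a slightly narrow confidence interval and a two-sided error rate slightly above 0.05. Correlated outcomes are most plausible for sexual and injection risk behavior, the secondary outcome. For PrEP adherence, the primary outcome, the documents give no basis for a partner correlation.

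**Working it through.** **Inputs from the documents.** N = 300 (150 per arm), two-sided alpha 0.05, d = 0.37, within-participant correlation 0.5 over five visits, stated power 98.5%, and 94.5% with 71% retained at 9 months.

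**Assumed, because the documents do not give them.** f, the share of participants enrolled with a partner; rho, the correlation between partners' outcomes; and the event rate.

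**1. The plan's own figures.** SE = sqrt((2/150) × (1 + 4 × 0.5)/5) = sqrt(0.008) = 0.0894. Power = Phi(0.37/0.0894 − 1.96) = 98.5%. Both match the plan (0.089 and 98.5%). The 94.5% is close to 93.6% with 213 retained (71% of 300) and 94.7% with the 224 that the plan also names. No couple correlation enters these figures.

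**2. Formula for ignored pairing.** Each partnered person adds one covariance term within the arm, so the variance is multiplied by 1 + f × rho. The true error rate is 2 × (1 − Phi(1.96/sqrt(1 + f × rho))).

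- f = 5%, rho 0.5: multiplier 1.025, alpha 0.053
- f = 10%, rho 0.5: 1.05, alpha 0.056
- f = 20%, rho 0.5: 1.10, alpha 0.062
- Alpha of 0.06 needs f × rho = 0.086. That is f = 17.2% at rho 0.5 (about 52 of 300 people) or 28.7% at rho 0.3 (about 86).

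**3. Effect on power.** Phi((1.96 + z)/sqrt(1 + f × rho) − 1.96), where z is the normal quantile of the stated power, at rho 0.5: 98.5% becomes 98.3% (f = 5%) and 97.6% (f = 20%); 94.5% becomes 94.0% and 92.4%.

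**4. Does the factor help when couple status does not predict outcome?** Simulation under the null: N = 300, event rate 0.4 in everyone, each single or couple allocated as one unit with probability 0.5, Wald test, 200,000 runs per row, Monte Carlo SE 0.0005.

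| Retention | f | rho | No factor | Factor | Couple-clustered |
|---|---|---|---|---|---|
| 100% | 0 | – | 0.050 | – | 0.049 |
| 100% | 6% | 0.5 | 0.052 | 0.052 | 0.048 |
| 100% | 10% | 0.5 | 0.055 | 0.056 | 0.049 |
| 100% | 20% | 0.5 | 0.061 | 0.062 | 0.050 |
| 100% | 20% | 0.3 | 0.056 | 0.057 | 0.049 |
| 71% | 6% | 0.5 | 0.051 | 0.051 | 0.048 |
| 71% | 20% | 0.5 | 0.057 | 0.058 | 0.049 |

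At full retention and rho 0.5, the unclustered SE divided by the true spread is 0.985, 0.973 and 0.950 at f = 6%, 10% and 20%. The formula 1/sqrt(1 + f × rho) gives 0.985, 0.976 and 0.953.

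A smaller simulation (10,000 runs, event rate 0.5) used the factor and clustering together. At f = 20%, rho 0.5 it gave 0.063 without the factor, 0.064 with it, and 0.053 with the factor plus clustering.

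**5. And when couple status does predict outcome?** Assumed event rates 0.7 in partnered and 0.4 in single participants, f = 20%, 40,000 runs, Monte Carlo SE about 0.001. Clustering here is without the factor.

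| rho within status | No factor | Factor | Clustered |
|---|---|---|---|
| 0 | 0.055 | 0.049 | 0.049 |
| 0.3 | 0.060 | 0.056 | 0.049 |
| 0.5 | 0.066 | 0.062 | 0.050 |

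The factor removes the part of the inflation that comes from a shared mean. The part that comes from residual correlation between partners remains.

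**The case against.** **Every adverse number is assumed.** Each partner must be in methadone treatment and meet the criterion "Were confirmed to be HIV-negative and started on PrEP in the past week". That may keep couples few, and nothing in the documents suggests that 17-29% of participants would be partnered. This stands and is why the point is minor.

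**Clustering shows no clear gain at the trigger.** At f = 6% and rho 0.5 the error rate is 0.0520 unclustered and 0.0483 clustered; at 71% retention, 0.0513 and 0.0482. This also stands. The benefit appears only well above 5%.

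**The factor does something useful.** A reader might infer that it is worthless and should be deleted. Step 5 does not support that: if couple status is prognostic, the factor removes part of the inflation, or all of it when no residual correlation remains. It should stay.

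**Part of the analysis text is missing.** A reader might infer that the plan nowhere models partner correlation. That cannot be said, because the alternative analysis is cut off and the word factor could have been meant as a random factor. The point is limited to the visible logistic models and to the rule as worded.

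**Couples may not be the main source of dependence.** Both conditions are delivered in groups, so members of one group may also be correlated. Couple-level clustering does not cover that.

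**The simulation is simpler than the trial.** It omits the stratified urn allocation, the neurocognitive-impairment covariate and the Bonferroni correction. The direction is secure; the third decimal is not.

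**Conclusion.** The point holds as a minor one. In the visible logistic models, a couple-status factor does not account for correlation between partners in the same arm, so the standard error of the arm comparison is slightly too small whenever that correlation is positive. At rho 0.5 the SE is about 1.5% too small at f = 6% and 5% at f = 20%. The corresponding error rates are about 0.052 and 0.062, against about 0.05 with clustering.

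A reader might go further and infer that the trial's error rate is materially inflated or that the primary adherence result is unsafe. The documents do not support that: they give no couple share and no partner correlation, the effect is negligible just above the trigger, and stated power falls by about one percentage point (98.5% to 97.6%) at f = 20% and rho 0.5. Confidence is medium, because the size rests on assumed f and rho and part of the analysis text cannot be read.

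**What to change.** Keep the couple-status factor as planned and add one sentence to the analysis plan:

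> Each participant carries a couple identifier (own identifier if no known enrolled partner), and outcome models use robust variance clustered on it.

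The clustering can apply whatever the share of couples, since it changes almost nothing when they are few. Staff must already recognise couples in order to allocate them together, so recording the link adds little work.

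The cost is one identifier per participant and somewhat wider confidence intervals: by simulation at full retention, about 0.2% with no couples, and at rho 0.5 about 1.6% at f = 6% and 4.9% at f = 20%. Couples unknown to staff, and dependence from shared intervention groups, remain uncovered.

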treatment care and being on PrEP will remain constant and the experimental CHRP-BB intervention will be compared to a time-and-attention-matched control condition. We will assess participants at baseline (T_0), immediately post-intervention (8 weeks; T_8) and follow-ups at 3- (T_{20}), 6- (T_{32}), and 9-month (T_{44}) post-intervention measurement points. This approach will allow us to examine whether CHRP-BB outcomes are superior to the Control condition in the short-term as well as examining the trajectory of PrEP adherence and HIV risk reduction over time. Importantly, this approach will allow a clear examination of the decay and/or emergence of intervention effects.^[5] The proposed research is also designed to allow us to precisely examine the relative cost and cost-effectiveness of each intervention with regard to both individual (efficacy: e.g., PrEP adherence, HIV risk reduction behavior) and population-level health outcomes (effectiveness: e.g., new HIV infections prevented, life years gained, quality of life). Importantly, we will also examine the barriers and facilitators to optimal implementation of the CHRP-BB intervention.

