Hypotheses related to the specific aims: This study is designed to test the primary hypothesis for PWUD prescribed PrEP that the experimental intervention (E=CHRP-BB) is significantly more effective vs. the control condition (S: time-and-attention matched intervention), for the primary outcome of high levels of PrEP adherence (e.g., ≥ 700 fmol/punch or ≥ 4 pills/week)^[25, 26] and secondary outcome of HIV risk reduction behavior. The null hypothesis is that CHRP-BB is not superior to control condition, expressed as $H_0: p_E = p_S$, where p_E is the proportion of participants in CHRP-BB who demonstrate high levels of adherence (e.g., ≥ 700 fmol/punch or ≥ 4 pills/week)^[25, 26] and are free from HIV risk behavior T₃₂post-intervention. Our alternative hypothesis is that the experimental intervention is superior to the control condition, and is expressed as $H_1: p_E > p_S$. Prior to analyzing treatment effects, the degree of pre-test equivalence between experimental and control groups on key variables (e.g., baseline demographics and clinical characteristics) will be evaluated. Baseline data will be evaluated via t-tests and ANOVAs on continuous items when normal or Kruskal-Wallis when we have a non-normal distribution of those items and chi-square tests of categorical items to evaluate pretest equivalence between and within the experimental and control groups. The presence of moderate/severe NCI will be included as a covariate to control for each of the dependent variables. We will use the Bonferroni approach^[43] to correct for alpha inflation with a 0.05 family-wise alpha. Variables in which inequality at baseline is identified will be used as covariates in further analyses to address potential non-equivalence across conditions.^[44] Differential attrition analyses will also be conducted on the data set to assess differential attrition by condition between baseline and subsequent measurements. A series of ANOVAs parametric or non-parametric of Condition (intervention, control) by Retention (retained, not retained) will be conducted on continuous pretest measures^[45]. Any variable influencing differential attrition will be included as a covariate in subsequent analyses.

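### The hypothesis is dated T32 (6 months) but the main outcome models are fitted at T44 (9 months), no visible text names one primary visit, and the stated power describes neither single-visit test

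*Combined protocol and SAP*

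**What the plan says.** **Visit.** Under Hypotheses related to the specific aims, the null and alternative are written on one proportion per arm, p_E and p_S. That proportion is defined by high adherence together with participants who "are free from HIV risk behavior T₃₂post-intervention". The Main outcomes analysis plan begins "The framework for testing the study hypotheses will be to compare differences between the two conditions" and then specifies its models. For adherence it says: "Separate logistic regression models will be used to assess the log odds of having high levels of PrEP adherence". The visit is given where the sentence turns to the risk outcome: "being free from injection or sexual transmission risk behaviors at T₄₄ post-intervention using intervention assignment as a binary coded predictor". The design paragraph lists the later follow-ups as "6- (T_{32}), and 9-month (T_{44}) post-intervention measurement points", so T32 and T44 are three months apart.

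**Outcome.** The hypothesis section ranks the outcomes. Adherence comes first, in the words "for the primary outcome of high levels of PrEP adherence". Risk behavior is ranked below it, in the words "and secondary outcome of HIV risk reduction behavior".

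**Power.** The power paragraph uses d = 0.37, a within-participant ICC of 0.500, 150 per arm and two-sided alpha 0.05. It reports 98.5% power with a standard error of about 0.089, and 94.5% if only 71% complete the 9-month visit. To keep its power it requires 258 retained at 6 months and 224 at 9 months.

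**The concern.** A confirmatory comparison needs one primary outcome at one visit. Here two analysts could follow two sections of the same plan in good faith, report different primary results, and each cite the protocol. The design paragraph says the schedule lets the investigators examine whether effects fade or emerge later, so the plan itself allows for the visits to differ. Even with an identical true effect, chance alone can make one visit significant and the other not. A choice of visit made then could not be shown to be independent of the data.

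Two smaller matters follow. The single p_E, read literally, joins adherence and freedom from risk behavior, whereas the models treat them separately. And a reader would attach 98.5% power to the primary test, although that figure appears to describe a repeated-measures average.

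**Working it through.** **1. Reproducing the stated power.** Inputs from the power paragraph: d = 0.37, ICC = 0.5, N = 300, two-sided alpha 0.05. The number of assessments m is not stated. For the mean of m assessments, SE = sqrt[(4/N) × (1 + (m − 1) × ICC)/m] and power = Φ(d/SE − 1.960).

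- m = 5, N = 300: SE = sqrt[(4/300) × 3/5] = 0.0894; d/SE = 4.137; power 98.5%. Both stated figures are matched.
- m = 4, N = 300: SE = 0.0913; power 98.2%. The power is close, but the standard error is not 0.089.
- m = 5, N = 224: 94.7% (94.5% with the t distribution). m = 5, N = 213 (71% of 300): 93.6%.

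So 98.5% is sound arithmetic for an average over repeated assessments. Five assessments would include baseline, while the PrEP adherence measures section schedules the blood-spot assay at four post-baseline visits.

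**2. One visit, d as a continuous difference.** Mean Z = 0.37 × sqrt(N/4); power = Φ(mean Z − 1.960).

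| Visit | N | Mean Z | Power |
|---|---|---|---|
| T32 | 258 | 2.972 | 84.4% |
| T44 | 224 | 2.769 | 79.1% |
| T44, 71% retained | 213 | 2.700 | 77.0% |
| All 300 at one visit | 300 | 3.204 | 89.3% |

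**3. One visit, binary outcome.** The documents give no control rate, so 10% to 80% is assumed. With n per arm, power = Φ[(Δ − 1.960 × s0)/s1], where s0 is the pooled and s1 the unpooled standard error of the difference in proportions.

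- Cohen's h = 0.37: about 83-84% at T32 and 77-79% at T44.
- Logit conversion, odds ratio = exp(0.37π/√3) = 1.96: about 45-76% at T32 and 40-70% at T44. For example, a 50% control rate becomes 66.2%. With n = 129, s0 = 0.0614 and s1 = 0.0606, so power = Φ[(0.1618 − 0.1204)/0.0606] ≈ 75%.

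**4. How often the visits disagree.** Take the two test statistics as bivariate normal with means 2.972 and 2.769. Then P(exactly one exceeds 1.960) = P(T32) + P(T44) − 2 × P(both). The correlation is an assumption; 0.5 is borrowed from the ICC.

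- Correlation 0.5: P(both) = 0.70966, so 0.84413 + 0.79070 − 2 × 0.70966 = 0.2155, about 22% (T32 only 13.4%, T44 only 8.1%).
- Correlation 0.3: 25.3%. Correlation 0.8: 14.0%.
- If T44 completers are a subset of T32 completers, 0.5 becomes 0.5 × sqrt(224/258) = 0.466, giving 22.2%.

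**The case against.** **The visit may date only one clause.** In the hypothesis section T32 directly follows the risk-behavior wording, which is the secondary outcome. A reader might infer that the primary hypothesis is firmly set at T32; the grammar does not prove that. The objection limits the claim without removing it: on this reading the risk outcome still moves from T32 to T44, and adherence has no visit in the hypothesis.

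**Text is lost.** The Main outcomes analysis plan breaks off inside an alternative plan for adherence. That plan may be a longitudinal model to which the power paragraph refers. This stands, and it is why the mismatch is not called a miscalculation. But the lost plan is labelled alternative, and the main models are dated T44.

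**A joint primary endpoint.** A reader might infer one from p_E. The explicit ranking of outcomes and the separate models point instead to loose drafting. Joint-endpoint power would need success rates that the documents do not give.

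**Inflated type I error.** If either visit could be declared primary without correction, the error would be about 9.1% at correlation 0.5. The plan states no such rule. It does state a Bonferroni approach "to correct for alpha inflation with a 0.05 family-wise alpha". Its scope is unclear, because the sentence sits among the baseline-comparison text, but that calls for clarification and does not show an error.

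**Conclusion.** The visit conflict is real and rests on the text alone. The hypothesis carries T32, the framework that tests it carries T44, and nothing visible names one primary visit. Its practical size is a 14-25% chance that exactly one visit is significant, about 22% at correlation 0.5. This assumes the same d = 0.37 at both visits, d read as a continuous difference, the planned retention, and test correlations from 0.8 down to 0.3.

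The power point holds in a limited form. The 98.5% and 94.5% fit a repeated-measures average and do not describe the single-visit logistic test. A reader might take 84% and 79% as the correct replacements. The documents do not support that, since d is not tied to a control rate and the logit conversion gives clearly lower values.

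**What to change.** Before unblinded outcome data are seen:

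1. Name one visit as primary for high PrEP adherence, use it in both the hypothesis section and the Main outcomes analysis plan, and label the other visits secondary. The blood-spot assay is scheduled at both T32 and T44, so either is feasible. T32 loses fewer participants; T44 tests longer durability.
2. Define p_E and p_S as the proportion with high adherence, and state freedom from risk behavior as a separate secondary hypothesis.
3. In the power paragraph, say that 98.5% (SE 0.089) and 94.5% refer to an average over repeated assessments, and give the number of assessments. If the single-visit logistic test stays primary, restate power for the binary outcome at the chosen visit with a stated control rate.
4. As a clarification, say which tests the Bonferroni correction covers.

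The cost is a text amendment to three places, with no added visits, data or participants. The downside is a less favourable stated power, and the visit not chosen becomes secondary.
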